1.2. Schema

Abbreviations: D = day; IV = intravenous; QW = once weekly; Q2W = every 2 weeks; Wk = week.

^a QW or Q2W dosing regimen depending on responder status. Responders (defined as participants with a decrease in clinESSDAI of ≥ 3 points from baseline of qualifying study or who have a change clinESSDAI score that reclassifies their disease from moderate severity to mild severity) will be switched from QW to Q2W dosing regimen. Nonresponders will remain on QW dosing regimen. Switch points (ie, timepoints where clinESSDAI are conducted to determine responder status) will occur on day 1, week 16, and week 24. If a participant is not a responder at week 24, they will be evaluated by the PI for therapeutic failure. If not considered a therapeutic failure, the participant will continue QW dosing regimen and will return at weeks 32, 36, 40 and 44 for a clinESSDAI assessment until confirming the responder status and switching to Q2W dosing regimen or PI considers the participant to be a therapeutic failure. For QW regimen, the final dose will be administered at week 47. For Q2W regimen, the final dose will be administered at week 46.

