Severity is classed as mild/ moderate/ severe/ life-threatening/ death. If a participant reports a TEAE more than once within that SOC/ PT, the AE with the worst-case severity will be used in the corresponding severity summaries.

Relationship, as indicated by the Investigator, is classed as “not related” or “related”. If a participant reports the same AE more than once within that SOC/ PT, the AE with the worst-case relationship to IMP will be used in the corresponding relationship summaries.

AEs leading to IMP discontinuation will be identified if “Drug withdrawn” is collected by using the “Action taken with Efgartigimod due to adverse event” from the AE page of the eCRF.

AEs leading to IMP interruption will be identified if “Drug interrupted” is collected by using the “Action taken with Efgartigimod due to adverse event” from the AE page of the eCRF.

Adverse event of special interest (AESsI) can be serious or nonserious, related, or unrelated to the IMP or study procedures. Infections are considered AESIs and are defined as events with a PT that falls under the MedDRA SOC ‘*Infections and infestations*’.

Infusion related reactions (IRRs) are defined as all AEs with a MedDRA PT that is listed in either:

Copyright © 2009, 2010, 2012, 2016, 2018, 2019, 2021, 2024 IQVIA. All rights reserved. The contents of this document are confidential and proprietary to IQVIA Holdings Inc. and its subsidiaries. Unauthorized use, disclosure or reproduction is strictly prohibited.

- MedDRA Hypersensitivity SMQ broad selection.
- MedDRA Anaphylactic reaction SMQ broad selection.
- MedDRA Extravasation events (injections, infusions and implants) SMQ broad selection, excluding implants. and occurs within 48 hours of an infusion/injection, or within 2 days if the AE start time is not available. In case of partially missing AE start date, the AE will be considered an IRR, unless the available parts of the AE start date provide evidence it did not occur within 48 hours of an infusion/injection.

Any deaths during the study are recorded on the “Deaths Details” page of the eCRF. A death case is defined as an AE with outcome ‘fatal’. Fatal events will be presented in a summary table presenting overall TEAEs and a data listing along with primary cause of death.

Summary tables will only include TEAEs. However, all AEs reported during the study will be listed. Summary tables by SOC and PT will be sorted alphabetically.

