An overview table of AEs will be presented by treatment to show number and percentage of participants with at least one event, the number of events, and the event rate per 100 patient years of follow-up (PYFU) for the following;

- TEAEs
- Serious TEAEs
- Grade ≥ 3 TEAEs
- Fatal TEAEs
- Treatment-related TEAEs according to the Principal Investigator
- Procedures-related TEAEs
- Serious treatment - related TEAEs
- TEAEs leading to IMP discontinuation
- TEAEs leading to IMP interruption
- TEAEs of Special interest
- IRRs

The event rate per 100 PYFU is defined as $100 * \frac{\text{number of events}}{\text{sum of the follow-up time during which an event is considered treatment-emergent of all participants expressed in years (i.e. divided by 365.25)}}$.

Some examples using the efgartigimod cut-off of 60 days:

With ‘the follow-up time during which an event is considered treatment-emergent’ we mean the following:

- If a participant received medication from Sept 1 until Sept 30, then the follow-up time during which events are considered treatment-emergent is from Sept 1 until 60 days after Sept 30. So, the follow-up time is 90 days.
- If a participant received only medication on Sept 1, then the follow-up time for this participant is 61 days.

Copyright © 2009, 2010, 2012, 2016, 2018, 2019, 2021, 2024 IQVIA. All rights reserved. The contents of this document are confidential and proprietary to IQVIA Holdings Inc. and its subsidiaries. Unauthorized use, disclosure or reproduction is strictly prohibited.

If a participant has no meaningful interruptions (ie, no interruptions of more than 60 days), the follow-up time during which an event is considered treatment-emergent is equal to (last dose date – first dose date + 1) + 60.

Example:

- Subject 1 has 2 TEAEs and a treatment duration (last dose date – first dose date +1) of 15 days => follow-up time = 15 + 60.
- Subject 2 has 1 TEAE and a treatment duration of 45 days => follow-up time = 45 + 60.

Then the event rate per 100 PYFU is calculated as: $100 * (2+1) / [(15+60+45+60)/365.25]$.

The actual duration of the event does not play any role in the derivation of event rate.

All AEs, including pretreatment events will be listed.

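### The overview table gives infusion-related reactions a rate per calendar time only, so the rate depends on dosing frequency; a rate per 100 infusions should be added beside it

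*SAP*

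**What the plan says.** SAP 17.1.1 defines an IRR as an adverse event with a term from one of three MedDRA queries "and occurs within 48 hours of an infusion/injection, or within 2 days if the AE start time is not available". There is one exception: "In case of partially missing AE start date, the AE will be considered an IRR, unless the available parts of the AE start date" show that it fell outside the window.

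The overview table in the same section shows, for each row, the participants with at least one event, "the number of events, and the event rate per 100 patient years of follow-up (PYFU) for the following" list, which ends with IRRs. One denominator serves every row: the "sum of the follow-up time during which an event is considered treatment-emergent of all participants expressed in years". Without an interruption of more than 60 days, a participant's follow-up "is equal to (last dose date – first dose date + 1) + 60".

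SAP 7.2 presents summaries overall and by parent-study treatment. The readable text has no adverse event table by regimen and no IRR rate per infusion. Regimen is set by clinESSDAI response, not by randomisation (Protocol 4.1, SAP 3.1). SAP 11 and 11.1 summarise the number of administrations per participant, pooled over regimens.

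**The concern.** The numerator is tied to infusions and the denominator to the calendar. Apart from partially dated events, an IRR can be counted only in the two days after an infusion, yet every day from first to last dose, plus 60 more, enters the denominator. A weekly (QW) participant has twice as many such windows as a two-weekly (Q2W) participant over nearly the same follow-up.

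IRRs are an adverse event of clinical interest (Protocol 8.4.7) in a study whose primary objective is long-term safety. The table is split by parent arm. Protocol 1.1 and 1.2 judge day 1 response against the baseline of the qualifying study, so the share on Q2W may differ between former efgartigimod and former placebo participants. (Protocol 4.1 words that reference point differently, which is a separate matter.) A reader could then take a difference in IRR rate for a difference in risk per infusion.

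**Working it through.** **Inputs.** IRR window of 48 hours and the follow-up formula: SAP 17.1.1. Final doses: "For QW regimen, the final dose will be administered at week 47. For Q2W regimen, the final dose will be administered at week 46" (Protocol 1.2). Dosing starts on day 1 (week 0). The risk of an IRR per infusion, *p*, is not in the documents; it is assumed equal at every infusion.

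**1. The SAP's own examples.** Dosing from 1 to 30 September: 30 + 60 = 90 days. A single dose: 1 + 60 = 61 days. Both agree with the SAP. Its rate example, left unevaluated, is 100 × 3 / (180/365.25) = 608.75 per 100 PYFU.

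**2. Completers.**

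| | QW | Q2W |
|---|---|---|
| Infusions | weeks 0 to 47: 48 | weeks 0, 2, …, 46: 24 |
| Day of last dose | 47 × 7 + 1 = 330 | 46 × 7 + 1 = 323 |
| Follow-up, days | 330 + 60 = 390 | 323 + 60 = 383 |
| Days in a 2-day window | 96 (24.6%) | 48 (12.5%) |
| Rate per 100 PYFU at *p* = 1% | 100 × 0.48 / (390/365.25) = 45.0 | 100 × 0.24 / (383/365.25) = 22.9 |
| IRRs per 100 infusions at *p* = 1% | 1.0 | 1.0 |

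The QW/Q2W ratio is (48/390) / (24/383) = 1.96 for any constant *p*. Participants who switch from QW to Q2W lie between: a switch at week 16 gives 32 infusions in 383 days (30.5 per 100 PYFU at 1%), and at week 24 it gives 36 (34.3).

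**3. Parent-arm columns** (regimen shares are assumptions; everyone completes on one regimen; *p* = 1%).
- 60% on Q2W: 0.4 × 48 + 0.6 × 24 = 33.6 infusions over 0.4 × 390 + 0.6 × 383 = 385.8 days, rate 31.8.
- 30% on Q2W: 0.7 × 48 + 0.3 × 24 = 40.8 infusions over 0.7 × 390 + 0.3 × 383 = 387.9 days, rate 38.4.
- Ratio 1.21 with equal risk per infusion. At 50% versus 40% it is 1.06; at 70% versus 20% it is 1.37.

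**4. The 60 days.** Without them the ratio is (48/330) / (24/323) = 1.96, so they do not cause it. They make up 60/390 = 15.4% (QW) or 60/383 = 15.7% (Q2W) of a completer's denominator and lower the rate by that share. After a last QW dose at week 23 (day 162) the share is 60/222 = 27%. After a single infusion, 61 days are counted and about 2 (3.3%) fall in a window.

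**5. If risk is not constant.** Suppose IRRs follow the first infusion only. The PYFU ratio QW/Q2W is then 383/390 = 0.98, while the per-infusion ratio is (1/48) / (1/24) = 0.50.

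**The case against.** **Events per patient-year are a legitimate measure.** Someone infused half as often at the same risk per infusion does have about half as many IRRs per year. That is a real difference in burden, and the SAP never calls its rate a risk per infusion. This stands, and it is a reason to keep the PYFU rate.

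**A per-infusion rate has its own assumption.** Step 5 shows that it distorts the regimen comparison if IRRs cluster at the first infusion. Former placebo participants receive their first efgartigimod of these studies here, so that pattern cannot be dismissed. This also stands: the per-infusion rate belongs beside the PYFU rate, not in its place.

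**Much can be derived already.** The same row carries the number and percentage of participants and the event count. SAP 17.1.1.1 tabulates IRRs and serious IRRs by term, SAP 11 summarises administrations, and Protocol 9.3.4 plans regimen counts by visit. A reader could form a crude per-infusion figure overall or by arm, but not by regimen at the time of the infusion.

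**Chance dominates.** With an assumed 20:10 split (the parent study's 2:1 ratio), the mixes of step 3 and *p* = 1%, expected IRRs are 20 × 0.336 = 6.7 and 10 × 0.408 = 4.1. The 95% Poisson factor on the rate ratio is exp(1.96 × √(1/6.72 + 1/4.08)) = 3.4 either way, far wider than 1.21. This limits the importance of the point; it does not make the column easier to interpret.

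**Conclusion.** The point holds. The IRR rate per 100 PYFU depends on dosing frequency, by a factor of about 1.96 between full-course QW and Q2W if risk per infusion is constant, and nothing in the table corrects for regimen mix between parent arms. The practical effect is modest: the study is descriptive, with up to about 30 participants, and the size of any parent-arm difference rests on assumed regimen shares.

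Stronger readings that a reader might infer are not supported:
- *The rate mainly reflects dosing frequency.* Frequency moves it at most about two-fold. The unknown risk per infusion matters more: from 0.1% to 2%, the QW rate runs from 4.5 to 89.9 per 100 PYFU, a 20-fold range.
- *Any parent-arm difference would be pure artefact.* The documents give no regimen shares, and fewer infusions do mean fewer IRRs per year.
- *No IRR can be counted outside 48 hours.* Partially missing start dates count by default.
- *The rows for events leading to discontinuation or interruption need first-to-last-dose time as denominator.* The SAP defines these by action taken ("AEs leading to IMP interruption will be identified if" the drug was recorded as interrupted), not by closeness to a dose. An event that leads to withdrawal often starts after what becomes the last dose; it would be counted while its day was left out. In the SAP's schematic (dosing on days 1–40 and 120–160), that denominator would also include days 41–119, when no dosing took place.
- *The tables by antidrug-antibody class share the fault.* SAP 15 names no PYFU rate for them.

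**What to change.** In the IRR row of the SAP 17.1.1 overview table, add IRRs per 100 infusions = 100 × number of IRRs / total IMP infusions administered, with infusions taken from the administrations derived in SAP 11.1. Show it overall and by parent arm, and preferably also by the regimen in force at the time of the infusion. Keep the number and percentage of participants, the event count and the PYFU rate.

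Footnote the row: the PYFU rate depends on dosing frequency and includes off-drug time; the per-infusion rate assumes roughly constant risk across infusions. Leave the other rows and the antidrug-antibody tables unchanged.

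The cost is a sentence in the SAP and one extra, footnoted entry in one table shell. No new data are needed. The split by regimen also requires each infusion to be labelled with the regimen under which it was given; SAP 11 already says that actual IMP allocation has to be considered when regimen is interpreted.

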IMP infusion ^m	X ⁿ	X ^{o,p}																	
AE review	Continuous monitoring																		
Concomitant medications review	Continuous monitoring																		

	BL ^a	Study week																EDV ^b	SFV ^c
		1	2	3	4	5-7	8	9-11	12	13-15	16	17-23	24	25-35	36	37-47	48		
Study day (±2)	1	8	15	22	29	36-50	57	64-78	85	92-120	127	134-162	169	176-246	253	260-330	337		393

BL = baseline; clinESSDAI = clinical; ESSDAI; D = day; d/c = discontinuation; ECG = electrocardiogram; EDV = early discontinuation visit; ESSDAI = EULAR Sjögren’s syndrome disease activity index; ESSPRI = EULAR Sjögren’s Syndrome Patient-Reported Index; EULAR = European Alliance of Associations for Rheumatology; ICF = informed consent form; IgG = immunoglobulin G; IMP = investigational medicinal product; IV = intravenous; MFI = Multidimensional Fatigue Inventory; NA = not applicable; OSS = ocular staining score; PASS = patient acceptable symptom state; PCR = polymerase chain reaction; PD = pharmacodynamics; PGA = patient global assessment; PK = pharmacokinetics; RF = rheumatoid factor; SCR = screening; SFV = safety follow-up visit; SF-36 = 36-Item Short Form Survey; SGUS = salivary gland ultrasonography; SS-A = Sjögren’s syndrome-related antigen A; SS-B = Sjögren’s syndrome-related antigen B; SWSF = stimulated whole salivary flow; UWSF = unstimulated whole salivary flow; W = week.

^a BL will coincide with the final visit of a previous qualifying study. Grayed-out assessments may be conducted as part of the previous qualifying pSS studies.

^b The EDV will be performed within 7 days after last dose administration.

^c Participants will attend a safety follow-up visit 56 ± 3 days after the final IMP administration.

^d Weight mandatory at baseline.

^e Vital signs will be measured before collecting any blood sample or administering IMP infusions.

^f On IMP administration visits, blood samples must be collected predose (preferably within 2 hours before the infusion). On other visits, a blood sample may be collected at any time during the visit.

^h On IMP administration visits, blood samples for PK analyses will be collected predose (preferably within 2 hours before IMP administration). On other visits, a blood sample may be collected at any time during the visit.

ⁱ A PK sample will also be collected within 30 minutes after the end of IMP infusion.

^j The biological domain will remain blinded until the parent study is unblinded.

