8.4.1. Time Period and Frequency for Collecting AE and SAE Information

All AEs will be collected from the signing of the ICF until the SFV, as specified in the SoA (Section 1.3).

All SAEs and AESIs will be recorded and reported to the sponsor or designee immediately, and under no circumstance it will exceed 24 hours, as indicated in Appendix 3 (Section 10.3). The investigator will submit any updated SAE data to the sponsor within 24 hours of being available.

Investigators are not obligated to actively seek information on AEs or SAEs after the conclusion of the study participation. However, if the investigator learns of any SAE, including death, at any time after a participant has been discharged from the study, and they consider the event to be reasonably related to IMP or study participation, the investigator must promptly notify the sponsor.

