9.4. Interim Analysis

An interim analysis may be conducted to support regulatory submissions if considered necessary by the sponsor.

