4.2. Interim Analysis

One interim analysis will take place after all enrolled subjects of ARGX-112-2211 study complete week 16 or discontinue prior to week 16.

The interim analysis will be performed by IQVIA Biostatistics following authorization of this SAP, database lock, and analysis sets.

Copyright © 2009, 2010, 2012, 2016, 2018, 2019, 2021, 2024 IQVIA. All rights reserved. The contents of this document are confidential and proprietary to IQVIA Holdings Inc. and its subsidiaries. Unauthorized use, disclosure or reproduction is strictly prohibited.

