11. STUDY MEDICATION EXPOSURE

Exposure to IMP in days will be summarized for the SAF.

The infusion start date/time and infusion end date/time of each dose administered along with total dose administered at each visit will be recorded. The date of first study infusion will be taken from the eCRF “Exposure - Infusion” form. The date of last study infusion will be taken from the eCRF “End of Treatment” form. Interruptions, temporary discontinuation, compliance, and dose changes are not considered for duration of exposure.

Table D: Treatment Administered Duration and the number of Administered doses.

The treatment exposure into different dosing regimen are described in the below table:

Classification based Dosing	Regime pattern
-----------------------------	----------------

[figure not shown]

Participants continuing QW (QW)	Start : QW During the study : QW End of study at week 48 : QW
Participants switching to and continuing Q2W (Q2W)	Start : Q2W During the study : Q2W End of study at week 48 : Q2W
Participants switching to Q2W at start of OLE and switching to QW (SQW)	Start : Day 1- Q2W During the study : The participant becomes a non-responder at week 16, 24, 32, 36, 40, 44, or an unscheduled visit where which a clinESSDAI result has resulted a non-responder outcome End of study at Week 48 : QW
Participants continuing QW and switching to Q2W later during OLE (SQ2W)	Starts: Day 1 – QW During the study: the study the participant becomes a responder at week 16, 24, 32, 36, 40, 44, or an unscheduled visit where which a clinESSDAI result has resulted a responder outcome -Q2W End of study at week 48 : Q2W

The above definitions do not consider authorized temporary discontinuation of treatment. Note the disease worsening is only recorded on the ECRF on weeks 24, 32, 40 and 44 or unscheduled. For more accurate interpretation of the regimen the actual imp allocation must be considered. Where a scheduled imp allocation has not occurred due to procedure or a missed visit, it will be considered as being undertaken for the purpose of checking the regimen period. Note: further detail may be required depending on the data received and this will be detailed within the ADAM Specifications.

Treatment Administration Duration will be defined overall from Start Day 1 to end of treatment or end of study.

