17.1.2.1. Laboratory Specific Derivations

All datapoints obtained after informed consent up to 60 days after IMP discontinuation will be considered.

- The following abnormality categories will be defined:
 - Low: value < lower limit of normal range
 - Normal: lower limit of normal range \leq value \leq upper limit of normal range
 - High: value > upper limit of normal range
- Notes:
 - Classification will be done in standardized units, using non imputed values and limits.
 - For the worst-case analysis visits, as defined in [Section 6.4](#), an additional category low + high is defined in case there are both low and high post-baseline values.

Toxicity grades will be computed according to the National Cancer Institute (NCI) common toxicity criteria for adverse events (CTCAE) toxicity grading list (version 5.0). The implementation of these toxicity grades for analysis is presented in [Appendix 2](#). Only the parameters described in [Appendix 2](#) will be computed, according to the declared limits for each grade.

Only lab parameters specified within the protocol will be analysed and, only those both in the protocol and in [Appendix 2](#) will be considered for toxicity. All others that are in the protocol and not in [Appendix 2](#), but have High/Low/Normal will be presented in the abnormality table.

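### The follow-up time behind the AE rate per 100 PYFU is not capped at study exit, death or data cut-off, so the rate is biased downward: slightly at the final analysis, possibly materially at the week 16 interim

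*SAP*

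**What the plan says.** SAP 17.1.1 puts an event rate per 100 patient-years of follow-up in the AE overview table, for TEAEs overall and for serious, grade 3 or higher, fatal, treatment-related and special-interest TEAEs among others. If a participant's dosing was never interrupted for longer than 60 days, the rule is this: "the follow-up time during which an event is considered treatment-emergent is equal to (last dose date – first dose date + 1) + 60". Every worked example adds the 60 days without condition; for instance, "If a participant received only medication on Sept 1, then the follow-up time for this participant is 61 days".

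The observation period is set elsewhere. Protocol 8.4.1: "All AEs will be collected from the signing of the ICF until the SFV". Protocol 1.3, footnote c: "Participants will attend a safety follow-up visit 56 ± 3 days after the final IMP administration". Protocol 7.2 defines study withdrawal as the end of all assessments.

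On the interim, SAP 4.2 says: "One interim analysis will take place after all enrolled subjects of ARGX-112-2211 study complete week 16 or discontinue prior to week 16". Protocol 9.4 says: "An interim analysis may be conducted to support regulatory submissions if considered necessary by the sponsor". SAP 11 gives the source of the last dose date: "The date of last study infusion will be taken from the eCRF “End of Treatment” form".

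**The concern.** A person-time denominator should contain only time in which an event could have been recorded. Under the formula, a participant who withdraws, dies or is lost shortly after a dose still contributes a full 60 days. Even a completer is credited past the safety follow-up visit, because 53 to 59 days is always less than 60. Unobserved days add to the denominator and no systematically collected events to the numerator, so the error has one direction: the rate looks lower and the drug safer. Long-term safety is the primary objective.

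The largest exposure is the week 16 interim. A participant still on treatment would be credited with up to 60 days that lie after the cut. The SAP states no data cut rule and no list of interim outputs. It also takes the last infusion date from a form that a participant still on treatment would not be expected to have.

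**Working it through.** **The SAP's own figures.** Follow-up = (last dose − first dose + 1) + 60; rate = 100 × events / (total days / 365.25).

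- Dosing 1 to 30 September: 30 + 60 = 90 days. Single dose: 1 + 60 = 61 days. Both agree with SAP 17.1.1.
- Rate example: 100 × 3 / [(15 + 60 + 45 + 60) / 365.25] = 608.75 per 100 PYFU.

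**Measure of bias.** With events unchanged, rate as written / capped rate = observed days / credited days. One minus this ratio is the proportion by which the rate is too low.

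**Final analysis, completers.** The last scheduled dose is week 47 for QW (day 7 × 47 + 1 = 330) and week 46 for Q2W (day 7 × 46 + 1 = 323), so credited time is 390 and 383 days.

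| Safety follow-up after last dose | QW | Q2W | Rate too low by |
|---|---|---|---|
| 53 days | 383/390 = 0.982 | 376/383 = 0.982 | 1.8% |
| 56 days | 386/390 = 0.990 | 379/383 = 0.990 | 1.0% |
| 59 days | 389/390 = 0.997 | 382/383 = 0.997 | 0.3% |

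**Final analysis with withdrawals.** The documents give no dropout rate. Assume 30 participants on QW, the rest completing with the visit at 56 days, and leavers exiting on day 29 after a last dose on day 22 (credited 22 + 60 = 82 days).

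- One leaver: (29 × 386 + 29) / (29 × 390 + 82) = 11,223/11,392 = 0.985, 1.5% low.
- Three leavers: (27 × 386 + 3 × 29) / (27 × 390 + 3 × 82) = 10,509/10,776 = 0.975, 2.5% low.

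Participants who stop IMP but attend the safety follow-up visit add little.

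**Interim, one participant dosed on the cut day.** Week 16 is day 113 in the SAP visit windows: 113/173 = 0.653, 35% low. The protocol's Schedule of Activities prints day 127 for week 16: 127/187 = 0.679, 32% low.

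**Interim, pooled.** Assume 30 participants with evenly spaced entry, none discontinued early, and the cut when the last one reaches day 113. Observed time is the smaller of the cut day and last dose + 56. Credited time is last dose by the cut + 60.

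| Accrual period (assumed) | Dosed on cut day | Actual QW dose days | Actual Q2W dose days | Rate too low by |
|---|---|---|---|---|
| 3 months | 0.726 | 0.737 | 0.748 | 25% to 27% |
| 6 months | 0.773 | 0.784 | 0.794 | 21% to 23% |
| 9 months | 0.824 | 0.831 | 0.840 | 16% to 18% |
| 12 months | 0.873 | 0.879 | 0.887 | 11% to 13% |

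**Schedule conflict.** The Schedule of Activities prints day 393 for the safety follow-up visit. That is 393 − 330 = 63 days (QW) or 393 − 323 = 70 days (Q2W) after the last scheduled dose. Neither fits 56 ± 3 days, and both lie beyond the limit in SAP 17.1.2.1: "All datapoints obtained after informed consent up to 60 days after IMP discontinuation will be considered". The same 60-day limit applies to ECG and vital signs (SAP 17.1.3, 17.1.4).

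**The case against.** The strongest case against is about materiality.

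- **Small final effect, and a disputed visit date.** For completers the bias is at most 1.8%, in a descriptive study of about 30 participants with no hypothesis test. If day 393 is the real visit date, completers are observed beyond last dose + 60 and their bias is zero. The withdrawal scenarios then fall to 0.5% (11,339/11,392 = 0.995) and 1.5% (10,617/10,776 = 0.985). This stands. It does not remove the error for withdrawals, deaths or an interim cut.
- **The interim figures are conditional.** The SAP does not say that the overview table is produced at week 16, and accrual and cut date are assumed. If the last dose date is available only from the End of Treatment form, the formula cannot be run for participants still on treatment until another rule is set. Nor does the SAP tie this interim to a submission. All of this stands: the interim numbers illustrate one natural implementation. The missing input is itself a gap to close before a planned analysis.
- **A cap may be implied or sit elsewhere.** Follow-up time could be read as time actually followed, and the SAP's schematic does not test the point, since study discontinuation there (day 240) falls after the window closes (day 220). But the formula and examples are explicit and unconditional. SAP Appendix 1 and the output templates were not available for this review; a cap found there would settle the matter.
- **Narrow scope.** Only one measure in one table is affected. This is correct.

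**Conclusion.** The concern holds. Followed as written, SAP 17.1.1 credits time in which AEs were not collected, and the rate per 100 PYFU is biased downward. At the final analysis the size is about 1.0% for completers seen at 56 days (0.3% to 1.8% across the visit window; none if the visit is at day 393), and 1.5% to 2.5% in the assumed withdrawal scenarios. At the week 16 interim, if the rate is produced, it is about 11% to 27% too low when pooled, depending on the assumed accrual period; the 35% figure is for a single participant. For participants with an interruption of more than 60 days, the text reviewed gives no cap either. The point should be corrected because the rate serves the primary safety objective and the error always favours the product, although its effect at the final analysis is small.

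**What to change.** In SAP 17.1.1, end each participant's treatment-emergent follow-up at the earliest of last dose + 60 days, end-of-study or withdrawal date, death, and data cut-off. Use the same limit for the events counted, at both the interim and the final analysis.

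In SAP 4.2, state the data cut date, take the last dose on or before it from the Exposure - Infusion form, and say whether the PYFU rate is produced at the interim.

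Reconcile day 393 in the Schedule of Activities with footnote c and with the 60-day limit for laboratory, ECG and vital-sign data.

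The cost is one line in the SAP and in the ADaM derivation, a short statement on the interim, and a clarification of the schedule. No new data are needed. The downside is that reported rates rise slightly and will not match any other study report that uses the uncapped formula.
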